726 If cisplatin regimen is discontinued or de-escalated to a lower dose of cisplatin or changed to a different cytotoxic or non-cytotoxic agent, metformin will be continued unless metformin related toxicity is observed and the data from that patient will be recorded as part of the study as long as the patient can continued to receive the prescribed dose of radiation.

7.2.5 If radiation is terminated prior to completion of the prescribed standard of care dose, metformin will be stopped.

7.3 Radiation dose modification

Consistent with current institutional and national standards, de-escalation of the radiation component will not be allowed during the protocol. Adjustments to specific components of the radiation field will be allowed at the discretion of the treating radiation oncologist based on tumor response, consistent with current institutional practice protocols. Treatment breaks must be clearly indicated in the treatment record along with the reason(s) for the treatment break(s). Treatment breaks should be allowed only for resolution of severe acute toxicity and/or for inter-current illness and not for social or logistical reasons. Missed treatments due to holidays or for logistic reasons can be compensated for by delivering an additional treatment (BID, two fractions in one day at least 6 hours apart) during the week, or treating on the Saturday or Sunday of that week, or adding to the end of treatment.

8 CORRELATIVE STUDIES (Optional For Patients)

NOTE: Optional correlative studies have been removed from the protocol with R10 due to insufficient evaluable data being available to draw meaningful conclusions.

9 TREATMENT EVALUATION

9.1 Pre-treatment evaluation

- 9.1.1 A complete history and physical examination by a medical, radiation or surgical (ENT or Head and Neck Surgery) oncologist, and baseline laboratory studies, including complete blood count (CBC), complete metabolic panel (CMP) and fasting glucose or non-fasting HgbA1c will be performed within 30 days of starting metformin escalation. Negative pregnancy test is required 10-14 days before registration for women of child bearing age who maintain reproductive potential (i.e. have not undergone hysterectomy).
- 9.1.2 Sample collection for baseline correlative studies will be performed before initiation of metformin escalation as outlined in the study calendar.
- 9.1.3 One of the following combinations of imaging is required within 8-12 weeks prior to registration:

- a) A CT scan of the neck (with contrast) and a chest CT scan (with or without contrast), or
- b) A CT scan of neck (with contrast) and a PET/CT of neck and chest (with or without contrast). **Note:** A CT scan of neck and/or PET/CT performed for radiation planning and read by a radiologist may serve as both staging and planning tools.

Staging (T, N, M) will be performed by the treatment team following diagnosis and discussion at multi-disciplinary tumor conference, per standard of care practice. For the purpose of the study, the clinical TNM staging for each patient will be obtained by the PI or clinical coordinator from the medical record and entered into the study prior to treatment initiation.

9.1.4 Evaluation by a nutritionist and/or swallowing therapist is highly recommended within 2-4 weeks prior to the start of chemo-radiation treatment and should include evaluation for placement of prophylactic gastrostomy or other type of feeding tube. The decision to place a feeding tube should be individualized and may consider a number of factors including: prior weight loss, current nutritional status, size and location of the primary tumor (impacting high dose target volume), availability of feeding tube placement services, availability of speech and swallowing specialists, and social support. Feeding tubes may be placed after start of treatment at the discretion of the clinical team. If a tube is placed, documentation will be provided in the patient's protocol file if the tube was placed prophylactically (as a preventative measure) or therapeutically (because of nutritional compromise or other clinical indications).

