iii. platelets	$\geq 100,000/\text{mcL}$
iv. total bilirubin	within normal institutional limits
v. AST(SGOT)	$\leq 2.5X$ institutional upper limit of normal
vi. ALT / (SGPT)	$\leq 2.5X$ institutional upper limit of normal
vii. creatinine $< 1.5\text{mg/dL}$ OR creatinine clearance $\geq 60 \text{ mL/min}/1.73 \text{ m}^2$ for patients with creatinine levels $>$ institutional normal	

- _____ m. Patients must be candidates for standard of care treatment consisting of chemotherapy (cisplatin) and radiation.
- _____ n. Willingness to Use Contraception: The effects of metformin on the developing human fetus at the recommended therapeutic dose are unknown. For this reason, women of child-bearing potential and men must agree to use adequate contraception (hormonal or barrier method of birth control; abstinence), 30 days prior to study drug initiation and 30days post completion of study drug administration. Should a woman become pregnant or suspect she is pregnant while participating in this study, she should inform her treating physician immediately.
- _____ o. Informed Consent: Patients must have the ability to understand and the willingness to sign a written informed consent document.
- _____ p. Patients may not be receiving any other investigational agents.
- _____ q. Brain metastases: Patients may not have diagnosed brain metastases.
- _____ r. Prior Allergies: Patients may not have a history of allergic reactions attributed to compounds of similar chemical or biologic composition to metformin.
- _____ s. Patients must not have a diagnosis of diabetes mellitus (DM) or be receiving active treatment for DM. If patient does not have known DM diagnosis, the patient must have either fasting glucose or hemoglobin A1C test within 30 days of registration. Patient is not eligible if glucose level \geq 126mg/dl or hemoglobin A1c \geq 6.0%. (Either test is sufficient for eligibility; both tests are not needed.)
- _____ t. Patients may not have an uncontrolled intercurrent illness including, but not limited to, ongoing or active infection, symptomatic congestive heart failure, unstable angina pectoris, cardiac arrhythmia, or psychiatric illness/social situations that would limit compliance with study requirements.
- _____ x. Patients may not be pregnant or breastfeeding.
- _____ y Patients may not have diagnosed HIV.
- _____ z. Patients may not be taking metformin for a reason other than study participation.

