5.0 REGISTRATION PROCEDURES

5.1 General Guidelines

- 5.1.1 Eligible patients will be entered on study centrally at the Clinical Trials Support Unit in the Dan L. Duncan Comprehensive Cancer Center at the Baylor College of Medicine by the Study Coordinator. Coordinators at each facility will discuss eligibility with the study PI. Patient eligibility checklist must be completed prior to enrollment. Study consent must be obtained prior to performing any study related procedures.
- 5.1.2 Following Registration, patient should begin treatment within 30 days. Issues that would cause treatment delays should be discussed with the Principal Investigator.

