9.2 Study Calendar

	Pre-study	wk -2 (d3+/-2d)	wk 1 (d3+/-2d)	wk 2 (d3+/-2d)	wk 3 (d3+/-2d)	wk 4 (d3+/-2d)	wk 5 (d3+/-2d)	wk 6 (d3+/-2d)	wk 7 (d3+/-2d)	30 days post radiation completion	Post-study (wk17+/-2wk)	Post-study (yr1 Q3mos)	Post-study (yr2 Q4mos)
Metformin tx		<-----BID metformin----->											
Chemo-radiation tx			<-----XRT (Daily); chemotherapy (weekly)----->										
Collected information (ONCORE)													
Metformin pill diary/compliance form		x	x	x	x	x	x	x	x				
Eligibility checklist	x												
Informed consent	x												
T, N, M staging	x												
Demographics	x												
Physical Exam	x	x	x	x	x	x	x	x	x		x	x	x
Medical history	x												
Vital signs	x										x	x	x
Weight	x	x	x	x	x	x	x	x	x		x	x	x
Performance status	x	x	x	x	x	x	x	x	x		x	x	x
Adverse event evaluation		x	x	x	x	x	x	x	x	x	x		
CMP	x												
CBC, BMP	x	x	x	x	x	x	x	x	x		x	x	x
Glucose monitoring (if applicable) (A)		x	x	x	x	x	x	x	x				
Disease response/radiologic evaluation											x	x	x
Pregnancy test	x (B)												
Imaging (C)	x										x	x	x
Laryngopharyngoscopy											x	x	x
pre-study items to be collected within 30 days of initiation of metformin treatment													
Pill diary/compliant may be discussed or completed via telephone.													
A: patients with hypoglycemia (<=60mg/dl) will receive instructions and supplies for BID glucose monitoring and recording													
B: Serum or urine pregnancy test (women of childbearing potential).													
C: Required within 8-12 weeks prior to registration, at end of radiation treatment, and at regular intervals following treatment completion.													
D= day, Wk= week, Mos= months, Yr= year; d3+/-2d= to be completed on day 3 of any given week, +/- 2days													

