18.0 ADVERSE EVENTS

18.1 Adverse Event Characteristics

18.1.1 The AE collection/reporting period will begin with the first day of treatment with metformin and will be completed at 30days following treatment completion. AEs after study registration but prior to the first day of study treatment will be captured as ongoing concurrent secondary diagnoses and symptoms present at the start of study. AEs will be graded in accordance with the NCI Common Terminology Criteria for Adverse Events v4.0 (CTCAE) <http://ctep.cancer.gov/reporting/ctc.html>. If not described in the NCI-CTCAE, AEs will be graded according to their severity using the following criteria: grade 1 (mild), grade 2 (moderate), grade 3 (severe), and grade 4 (life threatening).

18.1.2 This is the attribution scale which will be utilized to attribute relatedness of toxicity to the study:

- Definite – The AE is clearly related to the study treatment.
- Probable – The AE is likely related to the study treatment.
- Possible – The AE may be related to the study treatment.
- Unlikely – The AE is doubtfully related to the study treatment.
- Unrelated – The AE is clearly NOT related to the study treatment.

18.1.3 A definition of expected adverse event and unexpected adverse event:

18.1.3.1 Expected adverse events are those that have been previously identified as resulting from administration of the agent. For purposes of this study, an adverse event is considered expected when it appears in the current adverse event list in the Investigator's Brochure, the package insert, or is included in the informed consent document as a potential risk.

18.1.3.2 An adverse event is considered unexpected when it varies in nature, intensity, or frequency from information provided in

the current adverse event list in the Investigator's Brochure, the package insert or when it is not included in the informed consent document as a potential risk.

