APPENDIX B

Pregnancy testing guidelines and acceptable birth control methods

The safety of metformin in pregnant females has not been definitively established. Therefore, a risk minimization plan to prevent pregnancy must be observed.

Criteria for females of childbearing potential (FCBP)

This protocol defines a female of childbearing potential as a sexually mature female who: 1) has not undergone a hysterectomy or bilateral oophorectomy or 2) has not been naturally postmenopausal for at least 24 consecutive months (i.e., has had menses at any time in the preceding 24 consecutive months).

The investigator must ensure that:

- Females of childbearing potential comply with the conditions for pregnancy risk minimization, including confirmation that she has an adequate level of understanding
- Females NOT of childbearing potential acknowledge that she understands the hazards and necessary precautions associated with the use of metformin

Contraception

Females of childbearing potential (FCBP) enrolled in this protocol must agree to use a reliable forms of contraception simultaneously or to practice complete abstinence from heterosexual intercourse during the following time periods related to this study: 1) for at least 28 days before starting metformin; 2) throughout the entire duration of metformin treatment; 3) during dose interruptions; and 4) for at least 28 days after metformin discontinuation. FCBP must be referred to a qualified provider of contraceptive methods if needed. The following are examples of highly effective and additional effective methods of contraception:

Highly effective methods:

- oral contraceptive pills
- Intrauterine device (IUD)
- Hormonal (birth control pills, injections, implants)
- Tubal ligation
- Partner's vasectomy

Additional effective methods:

- Male condom
- Diaphragm
- Cervical Cap

The risk of venous thromboembolism continues for 4–6 weeks after discontinuing combined oral contraception. The efficacy of contraceptive steroids may be reduced during co-treatment with dexamethasone. Implants and levonorgestrel-releasing intrauterine systems are associated with an increased risk of infection at the time of insertion and irregular vaginal bleeding. Prophylactic antibiotics should be considered particularly in patients with neutropenia.

Pregnancy testing

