Medically supervised pregnancy tests with a minimum sensitivity of 50 mIU/mL must be performed for females of childbearing potential, including females of childbearing potential who commit to complete abstinence, as outlined below.

Before starting metformin

Female Patients:

FCBP must have one pregnancy tests (sensitivity of at least 50 mIU/mL) prior to starting metformin.

During study participation and for 28 days following metformin discontinuation

Female Patients:

At each visit, the Investigator must confirm with the FCBP that she is continuing to use a reliable method of birth control at each visit during the time that birth control is required. If pregnancy or a positive pregnancy test does occur in a study patient, metformin must be immediately discontinued. Pregnancy testing and counseling must be

performed if a patient misses her period or if her pregnancy test or her menstrual bleeding is abnormal. Metformin treatment must be temporarily discontinued during this evaluation.

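### Section 9.1.1, the study calendar and Appendix B time the baseline pregnancy test differently and define differently who is tested; they need to be reconciled into one rule

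*Combined protocol and SAP*

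**What the plan says.** The test enforces the exclusion of pregnant patients in section 4.0, criterion x, which gives no timing of its own. Timing appears in three other places.

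- **Section 9.1.1:** "Negative pregnancy test is required 10-14 days before registration for women of child bearing age who maintain reproductive potential". This range has a lower as well as an upper bound, and it is anchored to registration. The other baseline laboratory tests in the same paragraph are anchored to the start of metformin, with a 30-day limit.
- **Study calendar (the second section numbered 9.2):** the test is marked in the pre-study column only, under the general line "pre-study items to be collected within 30 days of initiation of metformin treatment". Its own footnote, "B: Serum or urine pregnancy test (women of childbearing potential"), gives no timing. Imaging, by contrast, has a separate window in footnote C.
- **Appendix B (pregnancy testing guidelines):** "FCBP must have one pregnancy tests (sensitivity of at least 50 mIU/mL) prior to starting metformin". No day limit is given.

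Section 5.1.2 sets the interval that links registration to dosing: "Following Registration, patient should begin treatment within 30 days".

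The women covered are also described differently. Section 9.1.1 refers to women of childbearing age with reproductive potential and names only hysterectomy as removing it. Appendix B names hysterectomy, bilateral oophorectomy and 24 months of natural menopause.

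**The concern.** A coordinator checking one test result meets three different rules. The lower bound in 9.1.1 means that a test done shortly before registration does not satisfy that section, while an older one does. Because 9.1.1 counts back from registration and the calendar counts back from metformin, a site can follow 9.1.1 and 5.1.2 exactly and still exceed the calendar's limit.

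At stake is the screening step that keeps pregnant women off two drugs. Section 4.0 (criterion n) calls the fetal effects of metformin unknown, and section 10.4 lists cisplatin as Pregnancy Category D. Eligibility is also verified under section 15.0, and a monitor would have no single standard for judging whether a given result was valid.

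**Working it through.** **Inputs**

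- Test to registration, *t*: 10 to 14 days (9.1.1).
- Registration to start of treatment, *s*: 0 to 30 days (5.1.2, worded as *should*).
- Calendar limit on the age of the result at first metformin: 30 days.
- Lead-in from metformin to radiation: about 14 days (6.4; phase I in 6.1, with a 24-hour allowance) or 1 week (phase II in 6.1).

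**Step 1. Age at first metformin if *treatment* in 5.1.2 means metformin.** Age = *t* + *s*.

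- Minimum: 10 + 0 = 10 days.
- Maximum: 14 + 30 = 44 days, which is 44 - 30 = 14 days over the calendar limit. The calendar's 30 days is therefore not reproduced by 9.1.1 and 5.1.2.

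**Step 2. How much of the permitted range exceeds 30 days.** There are 5 values of *t* and 31 of *s*, so 5 x 31 = 155 whole-day combinations. Those with *t* + *s* > 30 number 10, 11, 12, 13 and 14 for *t* = 10 to 14, which sum to 60. This counts permitted schedules. It is not a forecast of how many patients would be affected.

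**Step 3. When all rules agree.** *t* + *s* ≤ 30 requires *s* ≤ 30 - 14 = 16 for a test at day -14, and *s* ≤ 30 - 10 = 20 for a test at day -10.

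**Step 4. Age at first metformin if *treatment* in 5.1.2 means radiation.** Metformin then starts one lead-in earlier, so the maximum is 14 + 30 - lead-in.

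- 14-day lead-in: 14 + 30 - 14 = 30 days (31 if the 24-hour allowance shortens the lead-in to 13 days).
- 1-week lead-in: 14 + 30 - 7 = 37 days.

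**Step 5. Three illustrative patients** (days counted from registration, metformin taken as the start of treatment):

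| Test | Metformin | Age at dose | 9.1.1 | Calendar | Appendix B |
|---|---|---|---|---|---|
| -5 | +3 | 8 | not met | met | met |
| -14 | +30 | 44 | met | not met | met |
| -12 | +10 | 22 | met | met | met |

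The first row does not depend on how 5.1.2 is read; the lower bound alone produces it.

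**Step 6. Who is tested.** Appendix B counts a sexually mature woman if she lacks surgery *or* lacks 24 months of natural menopause. Read literally, failing to meet either exemption is enough, so a postmenopausal woman who has had no surgery still counts. Section 9.1.1 mentions neither oophorectomy nor menopause and relies on an unspecified childbearing age.

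**The case against.** The strongest reply is that the requirements are cumulative. A patient who starts metformin within 16-20 days of registration can satisfy all of them (Step 3), and a reader who applies the calendar as well as 9.1.1 is held to 30 days. That stands. A reader might infer that the passages cannot all be met, or that the protocol taken as a whole allows 44 days; the documents support neither. What remains is that 9.1.1 and 5.1.2 on their own permit what the calendar does not, and no passage says which governs.

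Other points on that side:

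- **The 44 days is conditional.** Section 5.1.2 does not say which treatment it means, and it says *should*, so 44 is not a hard ceiling. Section 18.1.1 supports the metformin reading ("The AE collection/reporting period will begin with the first day of treatment with metformin"), but the radiation reading is open.
- **The 10-14 days may be a drafting slip.** Sections 9.1.3 and 9.1.4 use ranges introduced by *within*, and the word may simply have been dropped here. That is plausible, and it is a reason to clarify the sentence.
- **A newer test is not forbidden.** A reader might infer that repeating the test breaches the protocol. Section 9.1.1 requires a test in its window and does not prohibit another.
- **There are safeguards after baseline.** Appendix B requires contraception to be confirmed at each visit, testing after a missed period or abnormal bleeding, and interruption of metformin during that evaluation. Section 19.0 withdraws a patient who tests positive. These reduce the risk, but none is a routine repeat test before the first dose.
- **Contraception periods.** A reader might see a conflict between section 4.0 ("30 days prior to study drug initiation and 30days post completion of study drug administration") and Appendix B ("1) for at least 28 days before starting metformin"). There is none: 30 days satisfies a minimum of 28.
- **Age at first cisplatin.** A reader might add the 14-day lead-in and report 44 + 14 = 58 days. With the one-week phase II lead-in it is 44 + 7 = 51, so no single figure is supported.

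**Conclusion.** The point holds as an inconsistency in a stated safety-screening rule. Two parts do not depend on how 5.1.2 is read: 9.1.1 literally excludes a test from the last 0-9 days before registration that the calendar and Appendix B would accept, and the group to be tested is defined differently in 9.1.1 and Appendix B.

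The size of the timing gap does depend on that reading. The oldest permitted result at first metformin is 44 days if treatment means metformin, and about 30-37 days if it means radiation, against 30 in the calendar. These figures treat the 30 days in 5.1.2 as a limit although it is worded as a recommendation, and they apply the calendar's general pre-study line to the pregnancy test because its footnote makes no exception.

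The documents give no number of women of childbearing potential, so the number affected cannot be estimated. Endpoints, sample size, alpha and power are untouched.

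**What to change.** The sponsor should reconcile sections 5.1.2 and 9.1.1, the study calendar and Appendix B so that one timing rule with one anchor applies throughout, and should state whether *treatment* in 5.1.2 means metformin or radiation. The sponsor should also confirm whether the 10-day lower bound in 9.1.1 is intended, and use one definition of childbearing potential in 9.1.1 and Appendix B, worded so that the effect of the *or* is unambiguous. Which window and which definition are right is the sponsor's clinical decision.

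The cost is a wording amendment and, depending on the rule chosen, possibly an occasional repeat test.

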12.1.2 Disease Parameters

Measurable disease. Measurable lesions are defined as those that can be accurately measured in at least one dimension (longest diameter to be recorded) as ≥ 10 mm with spiral CECT scan. All tumor measurements must be recorded in millimeters (or decimal fractions of centimeters).

Non-measurable disease. All other lesions (or sites of disease), including small lesions (longest diameter < 10 mm using spiral CECT scan), are considered non-measurable disease. Bone lesions, leptomeningeal disease, ascites, pleural/pericardial effusions, lymphangitis cutis/pulmonis, inflammatory breast disease, abdominal masses (not followed by CT or MRI), and cystic lesions are all non-measurable.

Target lesions. All measurable lesions up to a maximum of 5 lesions per organ and 10 lesions in total, representative of all involved organs, should be identified as target lesions and recorded and measured at baseline. Target lesions should be selected on the basis of their size (lesions with the longest diameter) and their suitability for accurate repeated measurements (either by imaging techniques or clinically). A sum of the longest diameter (LD) for all target lesions will be calculated and reported as the baseline sum LD. The baseline sum LD will be used as reference by which to characterize the objective tumor response.

Non-target lesions. All other lesions (or sites of disease) including any measurable lesions over and above the 10 target lesions should be identified as non-target lesions and should also be recorded at baseline. Measurements of these lesions are not required, but the presence or absence of each should be noted throughout follow-up.

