12.1.3 Methods for Evaluation of Measurable Disease

All measurements should be taken and recorded in metric notation using a ruler or calipers. All baseline evaluations should be performed as closely as possible to the beginning of treatment and never more than 4 weeks before the beginning of the treatment. The same method of assessment and the same technique should be used to characterize each identified and reported lesion at baseline and during follow-up. Imaging-based evaluation is preferred to evaluation by clinical examination when both methods have been used to assess the antitumor effect of a treatment.

Spiral contrast enhanced CT. Spiral CT should be performed using the approved institutional head and neck protocol.

Ultrasound (US). When the primary endpoint of the study is objective response evaluation, US should not be used to measure tumor lesions. It is, however, a possible alternative to clinical measurements of superficial palpable lymph nodes, subcutaneous lesions, and thyroid nodules. US might also be useful to confirm the complete disappearance of superficial

lesions usually assessed by clinical examination.

Endoscopy. The utilization of this technique for objective tumor evaluation has not yet been fully and widely validated. Its use in this specific context require sophisticated equipment and a high level of expertise that may only be available in some centers. Therefore, the utilization of such a technique for objective tumor response should be restricted to validation purposes. However, such a technique may be useful to confirm complete pathological response when biopsies are obtained.

Tumor markers. Tumor markers alone cannot be used to assess response.

Cytology, Histology. These techniques can be used to differentiate between partial responses (PR) and complete responses (CR) in rare cases (e.g., residual lesions in tumor types, such as germ cell tumors, where known residual benign tumors can remain). The cytological confirmation of the neoplastic origin of any effusion that appears or worsens during treatment when the measurable tumor has met criteria for response or stable disease is mandatory to differentiate between response or stable disease (an effusion may be a side effect of the treatment) and progressive disease.

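### The imaging window in Section 9.1.3 and calendar footnote C admits scans that Section 12.1.3 bars as the RECIST baseline, and the single scheduled pre-study scan can be the reference for PR.

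*Combined protocol and SAP*

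**What the plan says.** - **Section 9.1.3 (pre-treatment evaluation):** "One of the following combinations of imaging is required within 8-12 weeks prior to registration". The combinations are contrast neck CT with chest CT, or contrast neck CT with PET/CT. A Note adds that a scan "performed for radiation planning and read by a radiologist may serve as both staging and planning tools".
- **Study Calendar, footnote C:** "Required within 8-12 weeks prior to registration, at end of radiation treatment, and at regular intervals following treatment completion". The imaging row has one pre-study entry and none during treatment.
- **Study Calendar, general line:** "pre-study items to be collected within 30 days of initiation of metformin treatment".
- **Section 5.1.2:** "Following Registration, patient should begin treatment within 30 days".
- **Section 12.1.3:** baseline evaluations should be as close to treatment as possible and "never more than 4 weeks before the beginning of the treatment". It adds: "The same method of assessment and the same technique should be used to characterize each identified and reported lesion at baseline and during follow-up".
- **Section 12.1.2:** target lesions are to be measured at baseline, and "The baseline sum LD will be used as reference by which to characterize the objective tumor response".
- **Sections 12.1.4.1 and 13.2:** PR needs a decrease of at least 30% from the baseline sum of longest diameters (LD). CR or PR counts as a response; SD and PD do not.

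**The concern.** The section that tells a site which scan to obtain and the section that says which scan may be measured against use different limits and different anchors. One counts back from registration, the other from the start of treatment. A coordinator working from 9.1.3 and the calendar can accept a scan that 12.1.3 excludes as a baseline. Nothing in 9.1.3 or the calendar sends that coordinator to 12.1.3.

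This reaches the primary phase II endpoint through PR only. If the tumor grew between the scan and treatment start, a shrinkage that truly meets the PR threshold can be scored as SD, a non-response. If it shrank in that interval, a true SD can be scored as PR. CR means disappearance and does not depend on baseline size. A shift between SD and PD leaves the response count unchanged.

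Section 12.1.3 also does not say which start of treatment it means. Metformin begins 1 week before radiation in the phase II text of Section 6.1, and about 14 days before it in Section 6.4.

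**Working it through.** The plan states no figure to reproduce here. The check is date arithmetic, followed by an illustration with assumed inputs.

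**Inputs from the documents**
- Imaging window before registration (9.1.3, footnote C): 8 to 12 weeks, i.e. 8 × 7 = 56 to 12 × 7 = 84 days.
- Registration to treatment (5.1.2): 0 to 30 days, worded as a recommendation.
- Baseline limit (12.1.3): 4 × 7 = 28 days before treatment.

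**Scan age at treatment start = days from scan to registration + days from registration to treatment**

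| Reading of the 8-12 week window | Youngest scan | Oldest scan | Against the 28-day limit |
|---|---|---|---|
| Literal: between 8 and 12 weeks | 56 + 0 = 56 d | 84 + 30 = 114 d | always outside, by 28 to 86 d |
| Loose: any time up to 12 weeks | 0 + 0 = 0 d | 84 + 30 = 114 d | recent scans meet both rules; the oldest are 114 − 28 = 86 d outside |

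The conflict is present on either reading. On the loose one it affects only some scans.

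**Anchor.** If treatment in 5.1.2 means metformin, the oldest scan at the first radiation fraction is 114 + 7 = 121 days with a 1-week lead-in, or 114 + 14 = 128 days with a 14-day lead-in. If it means radiation, the figure stays at 114.

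**Effect on a PR call (illustration only).** Let g = sum LD at treatment start ÷ sum LD on the old scan. The documents give no value for g; those below are assumed.
- A true 30% shrinkage from treatment start is read against the old scan as 1 − 0.7g.
- The true shrinkage needed for a PR call is 1 − 0.7/g.

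| g (assumed) | True 30% shrinkage reads as | True shrinkage needed for PR |
|---|---|---|
| 0.90 | 37.0% (PR) | 22.2% |
| 1.00 | 30.0% (PR) | 30.0% |
| 1.05 | 26.5% (SD) | 33.3% |
| 1.10 | 23.0% (SD) | 36.4% |
| 1.20 | 16.0% (SD) | 41.7% |

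Only patients without CR whose shrinkage lies near 30% can change category.

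**The case against.** The strongest reply is that the rules are cumulative. Section 9.1.3 can be read as a staging requirement: its Note speaks of staging and planning, and the text that follows concerns TNM staging. On that reading 12.1.3 already governs measurement, and only a cross-reference is missing. This stands in part. A reader might infer that a 114-day scan is a compliant RECIST baseline. It is not: it meets 9.1.3 and 5.1.2 and breaches 12.1.3. What remains is that the operational sections admit the scan, the calendar schedules no other pre-study imaging, and using the planning scan is optional.

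Three further inferences go too far.
- **A third imaging window.** The calendar's 30-day line covers pre-study items in general, while footnote C is specific to imaging and would ordinarily prevail. The line needs clarifying but is weak evidence of a separate limit.
- **Discovery only at study end.** The blinded radiology review takes place then, but Section 12.1.2 has target lesions measured at baseline and Section 15.0 provides monitoring of compliance and data accuracy. An earlier catch is possible, although no scan-date check is specified.
- **A ban on a second baseline scan.** The statement in Section 12.1 that no additional imaging will be done sits in a paragraph on post-treatment scans. The argument here does not rely on it.

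**Conclusion.** The inconsistency is real and should be corrected. A scan about 114 days old at treatment start satisfies 9.1.3 and 5.1.2 while exceeding the 12.1.3 limit by 86 days. On the literal reading every scan in the window exceeds it. The 114 days is not a hard ceiling, because 5.1.2 is a recommendation and its anchor is unclear.

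A reader might infer that the response rate is biased downward or that power is lost. The documents do not support either. They give no scan ages or tumor growth rates and do not describe the imaging behind the 40% null rate. Error in either direction is possible, CR is untouched, and the number of patients affected may be zero. The percentages in the second table depend wholly on assumed size changes.

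**What to change.** 1. Reconcile 9.1.3, footnote C and 12.1.3 so that the scan used for baseline target-lesion measurement meets the 4-week limit already in 12.1.3. Keep older scans for staging only. State that the calendar's general 30-day line sets no different imaging limit.
2. State one anchor for the start of treatment, either the first metformin dose or the first radiation fraction, and use it throughout. The choice decides whether a planning CT taken during the lead-in can qualify.
3. Where the diagnostic scan is too old, use the radiation-planning CT already allowed by the Note in 9.1.3. Conditions: read by a radiologist, taken before the chosen anchor, contrast-enhanced, and matched to the follow-up method (12.1.3, 9.3.4).
4. Record the baseline scan date and check it before treatment starts. Require no extra scan.
5. Where no qualifying scan exists, keep the patient in the primary analysis under 13.5.2 and report the number of out-of-window baselines. A response rate in the in-window subset is optional and descriptive only, since 13.5.2 does not let such subsets support efficacy conclusions.

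The cost is wording in two sections and the calendar, one date field and one reported count. Sample size, decision rule and number of scans do not change. The downside is a radiologist's read of some planning CTs, and some of these will not qualify, for example for lack of contrast.
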